7.1 Primary objective

The primary aim of this study is to evaluate the dose response relationship of LNP023 on the reduction in proteinuria versus placebo after 90 days of treatment.

7.1.1 Variables

The primary variable is the log ratio to baseline of urine protein to creatinine concentration ratio (UPCR), with the Day 90 (Visit 160) assessment being of primary interest.

For the primary analysis the UPCR measurements will be obtained from the 24h urine collection. Baseline is defined to be the last measurement prior to the start of study drug administration.

7.1.2 Descriptive analyses

UPCR (raw and log ratio to baseline) will be listed by treatment group, patient and visit/time and descriptive statistics will be provided by treatment and visit/time. Summary statistics will include mean (arithmetic and geometric), SD, CV (arithmetic and geometric), lower quartile (25% quantile) Q1, median, upper quartile (75% quantile) Q3, minimum and maximum as appropriate.

7.1.3 Statistical model, assumptions and hypotheses

The primary endpoint will be analyzed using a two-stage approach:

1. A change from baseline in log transformed UPCR at multiple timepoints will be analyzed using a Mixed Model of Repeated Measures (MMRM) model, as described below.
2. A global hypothesis will be tested for the day 90 timepoint, using the generalized Multiple Comparison Procedure and Modelling (MCP-Mod) approach described by [Bretz et al 2005 and Pinheiro et al 2014](#). MCP-Mod will be applied on the dose estimates and variance-covariance matrix obtained from the MMRM model. MCP-Mod has two steps. In the MCP step, the existence of a dose-response trend is assessed based on

multiple contrasts test. In the Mod step the dose-response curve and the ED90 will be estimated based on model averaging techniques. Further details are provided below.

In general, the analysis will have the following steps:

- a) Fit the MMRM model
- b) Perform the MCP test based on the dose estimates and variance-covariance matrix from the MMRM. This step will give us information regarding the contrast values and contrast correlation matrix (per candidate model and dose) and t-tests with corresponding p-values for each candidate model.
- c) Parametric bootstrap model averaging will be used to estimate the mean dose-response curve by dose and mean predicted difference between each LNP023 dose and placebo.

For all efficacy analyses, a one-sided type I error rate of 10% (equivalent to a two-sided type I error of 20%) will be employed. Correspondingly, two-sided 80% confidence intervals (CI) will be presented.

Mixed Model of Repeated Measures

Firstly, the log ratio to baseline in UPCR at multiple timepoints (day 30 and 90) will be analyzed using a Mixed Model of Repeated Measures (MMRM) model. This model will have treatment, timepoint (as study day to start of study treatment), study part (Part 1 or Part 2) and ancestry (Asian/non-Asian) as fixed effects, treatment*timepoint and timepoint*log(baseline UPCR) as interaction terms and baseline log UPCR as fixed covariate. The study part fixed effect will be only included at the final analysis and not during the planned IA at the end of treatment in Part 1. Timepoint will also be included as a repeated factor with an unstructured residual variance-covariance matrix to allow adjustment for correlations between timepoints within subject; if not possible, other appropriate covariance structures will be explored such as Autoregressive (AR(1)) and Compound symmetry.

The mathematical formula of this MMRM is given as follows:

$$\underline{y} = \beta_0 + \underline{\beta_1} \text{treatment} + \beta_2 \text{timepoint} + \beta_3 \text{studypart} + \beta_4 \text{ancestry} + \underline{\beta_5} \text{treatment} \\ * \text{timepoint} + \beta_6 \text{timepoint} * \log(\text{base UPCR}) + \beta_7 \log(\text{base UPCR}) + \underline{\varepsilon}$$

where,

- \underline{y} is vector of the log ratio to baseline in UPCR
- β_0 the fixed effect intercept
- $\underline{\beta_1}$ and $\underline{\beta_5}$ the vector coefficients of the corresponding parameters and $\beta_2, \beta_3, \beta_4, \beta_6$ and β_7 the coefficients of the corresponding parameters.
- $\underline{\varepsilon}$ the vector of residuals where $\underline{\varepsilon} \sim N(0, \mathbf{R})$ with \mathbf{R} is a 2×2 diagonal covariance matrix.

Model estimated means and their difference versus placebo (and its 80% CI) will be calculated for each dose level. These will be back-transformed to the original scale to give a geometric mean ratio (and its 80% CI) between each dose and placebo.

Graphical methods will be used to present the model estimated means of ratio to baseline and ratio to placebo (of the ratio to baseline) along with CIs.

Multiple Comparison Procedure and Modelling

Secondly, the existence of a dose-response relationship will be assessed using the MCP-Mod approach via multiple contrast tests based on the log transformed model estimated means at Day 90 and covariance matrix obtained from the MMRM.

The following global hypothesis will be tested for the day 90 timepoint at the one-sided 10% significance level, to assess whether LNP023 is different from placebo (where H_0 assumes no dose-response relationship and H_1 that a dose response relationship exists):

$$H_0: c_m^T \mu = 0 \text{ for all } m \text{ in } \{1, \dots, 6\} \quad \text{vs} \quad H_1: c_m^T \mu > 0 \text{ for at least one } m \text{ in } \{1, \dots, 6\}$$

where c_m^T is the vector of optimal contrasts coefficients for the m^{th} candidate dose response shape ($c_m^T \mathbf{1} = 0$) and μ is the vector of adjusted means (on the log transformed scale) for each treatment group from the analysis of primary endpoint at day 90, i.e. $\mu = (\mu_{\text{placebo}}, \mu_{\text{LNP023d}_1}, \dots, \mu_{\text{LNP023d}_n})^T$. The H_0 will be rejected if the maximum contrast test statistic is larger than the critical value (representing the multiplicity adjusted critical value for a one-sided significance level of 0.1).

The following candidate models will be used to derive contrasts:

- Model 1: Linear
- Model 2: Emax with ED50 at 5mg
- Model 3: Emax with ED50 at 50mg
- Model 4: Sigmoidal emax with ED50 at 25mg and Hill parameter (h) equal to 3
- Model 5: Sigmoidal emax with ED50 at 50mg and Hill parameter (h) equal to 3
- Model 6: Exponential with $\delta = 50$

Table 7-1 lists the mathematical formula corresponding to each of the above dose-response relationship models.

Table 7-1 Dose-Response Models

Model	$f(d, \theta)$	Guesstimates
Linear	$E_0 + \delta d$	
Emax	$E_0 + E_{\text{max}} d / (ED_{50} + d)$	ED50
Sigmoidal Emax	$E_0 + E_{\text{max}} d^h / (ED_{50}^h + d^h)$	ED50, h
Exponential	$E_0 + E_1 [\exp(\frac{d}{\delta}) - 1]$	δ

where d denotes the dose, E_0 is the placebo effect for $d=0$, δ denotes the scale parameter of the model and h denotes the Hill parameter.

The contrast test statistics will be calculated as standardized linear combinations of the estimated treatment effects using:

- (i) the optimal contrast coefficients

- (ii) the adjusted means and variance-covariance matrix from the MMRM analysis.

The multiplicity adjusted critical value for the one-sided 10% significance level will then be determined from the joint multivariate t-distribution of the optimal contrasts using the correlation between the test statistics. The null hypothesis is to be rejected if the maximum of all t-statistics is larger than the derived critical value.

Parametric bootstrap model averaging from 10,000 simulations will be used to estimate the dose-response curve, the ED90 and 80% confidence intervals for each dose as follows:

1. The parametric bootstrap procedure will be performed to draw a sample of mean responses for each dose (including placebo) from the multivariate normal distribution of the estimated means from the different dose groups (including placebo) obtained from the MMRM model and associated variance-covariance matrix, described above.
2. All candidate dose-response models shown in [Table 7-1](#) will be fitted to each simulated bootstrap resample using generalized least-squares (similar to [Pinheiro et al. 2014](#)), and the best fitting model will be selected for each resample using the gAIC criterion.
3. The estimates of the mean dose response over the dose range will be derived (all doses including placebo) for each resample using the best model for the respective resample, selected in Step 2. The difference in estimated dose response between each LNP023 dose and placebo will also be calculated and presented with the estimated ED90.
4. The above steps (1-3) will be repeated 10,000 times. The bootstrapped estimates and 80% confidence intervals will be derived based on the quantiles (median, 10th and 90th percentile) of the resampled distribution of the estimates generated. The percentage of times ED90 could not be estimated in the bootstrap samples will be stated. The CI for ED90 will be considered valid if the ED90 can be estimated in at least 60% of the bootstrap samples.

The MCP-Mod results for dose-response and dose estimates will be back-transformed from the log-scale after the analysis.

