11.4.2 Statistical model, hypothesis, and method of analysis

At the time of final analysis all data from Part 1 and Part 2 of the study up to day 90 will be pooled and analyzed for the primary analysis; the FAS set (up to Day 90) will be used. If the study is stopped at the end of Part 1, then the results of the interim analysis will become the final analysis results.

The primary endpoint will be analyzed using Multiple Comparison Procedure (MCP) methodology as described as part of MCP-Modelling (MCP-Mod) by [Bretz et al 2005](#) and [Pinheiro et al 2014](#).

A two stage approach will be taken for this analysis: first, change from baseline in log transformed UPCR at multiple time points will be analyzed using a Mixed Model of Repeated Measures (MMRM) model. UPCR is derived from the 24h urine collections at baseline, day 30 and 90. The results will be back transformed and presented on the original scale.

The model will include treatment, time point (as study day relative to start of study treatment), study part (Part 1 or Part 2) and ancestry (Asian/non-Asian) as fixed effects and baseline log UPCR as fixed covariate. Baseline is defined to be the last measurement prior to randomization. Treatment by time point and time point by baseline log UPCR will be included as interaction terms. Timepoint will be included as a repeated factor with an unstructured covariance matrix to allow adjustment for correlations between time points within patients.

Secondly, the following global hypothesis will be tested for the day 90 time point using the generalized MCP-Mod approach ([Pinheiro et al 2014](#)) at the one-sided 10% significance level to assess whether LNP023 is different from placebo:

$$H_0: c_m^T \mu = 0 \text{ for all } m \text{ in } \{1, \dots, 6\}$$

$$H_1: c_m^T \mu > 0 \text{ for at least one } m \text{ in } \{1, \dots, 6\}$$

where μ is the vector of adjusted means (on the log transformed scale) for each treatment group from the analysis of the primary endpoint at day 90 i.e. $\mu = (\mu_{\text{Placebo}}, \mu_{\text{LNP023 dose 1}}, \dots, \mu_{\text{LNP023 dose n}})^T$ and c_m^T is the vector of optimal contrasts coefficients for the m^{th} candidate dose response shape m , as described below.

- Model 1: Linear
- Model 2: Emax with ED50 at 5mg
- Model 3: Emax with ED50 at 50mg
- Model 4: Sigmoidal emax with ED50 at 25mg and Hill parameter=3
- Model 5: Sigmoidal emax with ED50 at 50mg and Hill parameter=3

- Model 6: Exponential with $\delta = 50$

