7.1.3.1 Handling of missing values/censoring/discontinuations

The primary analysis will include all available data up to the point of treatment discontinuation for patients who permanently discontinue the treatment or the study.

This method is valid and consistent under a missing at random (MAR) assumption (i.e. given the observed data [responses and covariates] the probability of drop-out does not depend on the unobserved responses). This implies that the primary analysis aims to estimate the treatment effect under the hypothetical scenario that all patients adhere to randomized treatment. Therefore, the MAR assumption implies that the UPCR measurements for patients who discontinue treatment would be similar to those from other similar patients if they had continued to take the treatment.

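### SAP 7.1.3 contradicts itself on the primary MMRM: the formula gives a diagonal residual matrix, while the text and the protocol require an unstructured one

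*SAP*

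**What the plan says.** The primary model uses two post-baseline values per patient, the log ratio to baseline in 24-hour UPCR at Days 30 and 90. On the residual covariance, the documents say:

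- **SAP 7.1.3, prose:** an "unstructured residual variance-covariance matrix to allow adjustment for correlations between timepoints within subject". If that cannot be fitted, "other appropriate covariance structures will be explored such as Autoregressive (AR(1)) and Compound symmetry".
- **SAP 7.1.3, formula for the same model:** R is a 2×2 "diagonal covariance matrix".
- **Protocol 11.4.2:** "an unstructured covariance matrix to allow adjustment for correlations between time points within patients". The protocol summary says the same.
- **SAP 7.2.3, secondary MMRMs:** unstructured, in a model described as similar to the primary one.

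SAP 7.1.3.1 then justifies the handling of missing data: "This method is valid and consistent under a missing at random (MAR) assumption", meaning that "given the observed data [responses and covariates] the probability of drop-out does not depend on the unobserved responses". The adjusted means and covariance matrix from this MMRM feed the contrast tests, the bootstrap dose-response curve and the ED90.

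**The concern.** A diagonal 2×2 matrix and an unstructured one are different models. The first sets to zero the correlation that the prose says must be estimated. If a programmer took the formula literally, a Day 30 value would inform the Day 90 treatment means only through the study-part and ancestry terms, which are shared across time. The conditioning on observed responses that SAP 7.1.3.1 relies on would be lost.

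Missing Day 90 values are expected:

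- Protocol 11.7 allows for up to 20% drop-out.
- SAP 7.1.3.1 excludes data after treatment discontinuation.
- SAP section 3 sets Day 90 visits after the IA2 cutoff to missing.
- SAP section 11 allows COVID-affected observations to be left out.

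None of the analyses listed in SAP 7.1.3.2 and 7.1.3.3 uses data collected after discontinuation, so the missing-data argument rests on this covariance matrix.

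**Working it through.** **1. The plan's own figure.** Protocol 11.7 claims at least 85% power for Part 1. Inputs: 12/8/8/12 patients, SD 0.7 on the log scale, a 50% reduction (ln 2 = 0.693) taken as reached at 200 mg, one-sided 10%, six candidate shapes. Simulating the multiple-contrast test (critical value 1.68, 36 df) gives 86.7% to 92.2% across the shapes. A pairwise 12 versus 12 comparison gives 87.4%. The claim reproduces. It is a single-time-point calculation and does not involve R.

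**2. The two matrices.** Unstructured R has three free terms: σ₁², σ₂² and σ₁₂. Diagonal R has two, with σ₁₂ = 0. AR(1) and compound symmetry both estimate a correlation, so neither is diagonal in general. With two time points a 2×2 matrix must be the within-patient one, so the formula cannot be read as block-diagonal across patients.

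**3. Large-sample bias under diagonal R.** Treatment and baseline both interact with time, so the Day 90 arm means come essentially from patients observed at Day 90. Let ρ be the Day 30–Day 90 residual correlation, σ the residual SD, and m the mean standardised Day 30 residual among patients still observed at Day 90. Then

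bias in (active − placebo) ≈ ρ × σ × (m_active − m_placebo).

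Assume a placebo drop-out probability of logistic(−2 + 2z), where z is the Day 30 log UPCR change in SD units. Averaging over a standard normal z gives about 22% drop-out and m_placebo = −0.290. With σ = 0.7:

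- *Placebo-only rule* (m_active = 0): 0.4 × 0.7 × 0.290 = 0.081, rising to 0.8 × 0.7 × 0.290 = 0.162.
- *Same rule in all arms*, Day 30 effect 0.8 × ln 0.7 = −0.285 (m_active = −0.197): 0.7 × 0.093 × ρ = 0.026 to 0.052.
- *Same rule, no drug effect*: the two m values are equal, so the bias is 0.

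With σ = 0.6 and a weaker rule (odds 0.17 at the mean, 1.5 logits per SD), m_placebo = −0.245. The placebo-only bias is then 0.6 × 0.245 × ρ = 0.06 to 0.12. Under the same rule in all arms, m_active = −0.164 and the bias is 0.6 × 0.081 × ρ = 0.02 to 0.04.

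**4. Simulation of the SAP model.** Five arms of 20, SD 0.7, true Day 90 reduction at 200 mg of 30%, 600 runs per row, maximum likelihood with each form of R:

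| Drop-out | ρ | Unstructured R | Diagonal R | Diagonal bias (log) |
|---|---|---|---|---|
| 20%, completely at random | 0.4 / 0.6 / 0.8 | 30.2 / 30.2 / 30.4% | 30.2 / 30.2 / 30.5% | −0.003 / −0.003 / −0.007 |
| Day 30 rule, all arms (placebo 22–24%, 200 mg 14–15%) | 0.4 / 0.6 / 0.8 | 30.6 / 30.5 / 30.2% | 29.1 / 27.1 / 26.3% | 0.012 / 0.041 / 0.051 |
| Day 30 rule, placebo only (22%; 200 mg 10%) | 0.4 / 0.6 / 0.8 | 29.5 / 29.5 / 29.9% | 23.6 / 20.7 / 17.9% | 0.088 / 0.125 / 0.159 |

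The Monte Carlo error is about 0.24/√600 = 0.01, so steps 3 and 4 agree. The largest bias is 0.159/0.232 = 0.69 of the model standard error. In a two-arm check with drop-out driven by baseline only, diagonal R gave 30.2–30.3%, which is no bias. Under completely random drop-out the only cost is precision: a standard error of 0.238–0.240 with diagonal R against 0.224–0.236 with unstructured.

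**The case against.** The strongest reply is that nobody reading the whole plan would fit a diagonal matrix. The protocol (twice), the SAP prose directly above the formula and SAP 7.2.3 all say unstructured. The purpose is stated, the fallbacks are both correlated structures, and nothing offers a diagonal matrix as an option. That stands: the line looks like a drafting slip, and the bias is conditional on literal programming.

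Four stronger readings are tempting, and the documents do not support them.

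- *The plan has given up its missing-at-random protection.* It has not. One line conflicts with every other statement of the model.
- *Diagonal R would lose all such protection.* It would still be unbiased when missingness depends only on modelled covariates (treatment, baseline UPCR, study part, ancestry). What goes is the conditioning on the Day 30 response.
- *A bias of around 10% is to be expected.* Values of that order need drop-out that follows Day 30 UPCR in placebo but not in the active arms. Nothing in the documents indicates this. A weaker placebo-only rule (0.5 logits per SD, SD 0.6, correlation 0.5–0.7) gives 0.02–0.03.
- *The IA2 result is wrong.* The documents do not show which matrix was programmed.

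**Conclusion.** The contradiction is real and lies in the definition of the primary analysis, so it should be corrected. Its consequence is conditional. If R were programmed as diagonal, the bias in the Day 90 contrast would be:

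- about 0 when drop-out is unrelated to Day 30 UPCR, or when the same rule acts in all arms and there is no drug effect;
- 0.02–0.05 log units when the same rule acts in all arms with a 30% effect;
- about 0.06–0.16 under a placebo-only rule.

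In these scenarios the direction is towards a smaller drug effect. Unstructured R gives about 0 throughout. The ranges rest on assumptions outside the documents: correlation 0.4–0.8, the form and strength of the drop-out rule, about 22% placebo drop-out, a 30% true effect, and SD 0.6 as the lower value (the protocol gives 0.7). Stated power and sample size are unaffected.

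**What to change.** In SAP 7.1.3, define R as a 2×2 unstructured (symmetric, positive-definite) covariance matrix within patient, with independence across patients. This matches the prose and the protocol and costs one phrase.

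Also confirm, and record, that the IA2 primary-analysis program used the unstructured matrix. SAP sections 3 and 7 treat that analysis as final and allow a re-run only as a sensitivity analysis if data discrepancies matter, so correcting the text alone would not reveal a programming error. The cost is one check of the covariance statement in the program. If the check shows a diagonal matrix, the analysis should be repeated with the structure that the protocol specifies, and both results reported.

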7.1.3.1 Handling of missing values/censoring/discontinuations

The primary analysis will include all available data up to the point of treatment discontinuation for patients who permanently discontinue the treatment or the study.

This method is valid and consistent under a missing at random (MAR) assumption (i.e. given the observed data [responses and covariates] the probability of drop-out does not depend on the unobserved responses). This implies that the primary analysis aims to estimate the treatment effect under the hypothetical scenario that all patients adhere to randomized treatment. Therefore, the MAR assumption implies that the UPCR measurements for patients who discontinue treatment would be similar to those from other similar patients if they had continued to take the treatment.

7.1.3.2 Supportive analysis

A supportive analysis may be performed considering the exclusion of subjects who have intercurrent events that may affect the primary analysis (for example, taking prohibited Concomitant Medications, listed in [Table.](#)), as well as under the cases with the following protocol deviations:

- a. “Subject taking medication such as Gemfibrozil or Strong CYP2C8 inhibitors with 5 half-lives of the inhibitor prior to administration of LNP023” (PD code “COMD08”)
- b. “Subject taking P-gp substrates with narrow therapeutic index with 1 day prior to administration of LNP023” (PD code “COMD09”)

As a separate supportive analysis, the following subgroup analyses will be performed for the FAS (up to Day 90):

- Baseline UPCr (24h sample) < 200mg/mmol and \geq 200 mg/mmol

Graphical methods, such as forest plots, will be used to present the model estimated means of ratio to baseline and ratio to placebo (of the ratio to baseline), for each of the analyses.

At the final DBL, discrepancies between the primary efficacy outcome data at IA2 and at DBL will be investigated and a listing of any discrepancies by subject, timepoint, UPCr24h value at IA2 and UPCr 24h value at DBL, will be produced. Discrepancies in data between the IA2 and final DBL will be assessed and if considered of impact, the MMRM related to the primary efficacy analysis may be reproduced if required.

7.1.3.3 Sensitivity analysis

A sensitivity analysis of the ratio to baseline of UPCr (24-hour urine collection) for Part 1 and Part 2 at Day 90 will be performed, by excluding the linear model from the Mod step.

Graphical methods of the estimated geometric mean UPCr ratio to baseline and dose response relationship at Day 90 (Parts 1 and 2) and the estimated geometric mean UPCr ratio to placebo (of ratio to baseline) and dose response relationship at Day 90 (Parts 1 and 2) will be produced.

7.2 Secondary objectives

The secondary aim of the study is to assess the effect of LNP023 on renal function.

7.2.1 Variables

The secondary variables are the following:

- Log ratio to baseline in UPCr (from 24hr urine up to Day 180)
- Log ratio to baseline in UPCr (from first morning void)
- Change from baseline in eGFR
- Change from baseline in Serum Creatinine

- Hematuria
- Log ratio to baseline in 24h-UP.
- Log ratio to baseline in 24h-UA
- Log ratio to baseline in UACR

The 24h-UP and 24h-UA will be derived using the following formula:

$$\text{True 24h parameter} = \frac{(\text{measured parameter content} \times 24)}{\text{length of time (in hour) sample collected over}}$$

Baseline is defined to be the last measurement prior to the start of study drug administration. Each secondary variable is derived from the 24h urine collections at baseline, day 30 and 90, except for the eGFR and Serum Creatinine which are derived from the blood measurements at baseline, day 1, 8, 15, 30 and 90 and UPCR and hematuria which are derived from FMV samples at baseline, day 1, 8, 15, 30, 60 and 90. For analyses on FAS2, measurements up to day 180 will be considered (additionally day 60 and 135 for eGFR and Serum Creatinine).

